5.2. SAFETY ENDPOINTS

Variable	Role	Operational definition		
Major bleeding event after index date	Outcome (primary endpoint)	Major bleeding after index date will be identified using hospital claims which had a bleeding diagnosis code as the first listed ICD-10 or disease code (Appendix 10.3.5). An event occurrence of major bleeding is defined as a case that "21: Disease name behind hospitalization" in DPC database. Time-to-major bleeding will be defined as the number of days from the index date to the occurrence of the first major bleeding event.		
Major ICH bleeding event after index date	Outcome (secondary endpoint)	Major ICH bleeding after index date will be identified using hospital claims which had an ICH bleeding diagnosis code as the first listed ICD-10 or disease code (Appendix, 10.3.4). An event occurrence of major bleeding is defined as a case that "21: Disease name behind hospitalization" in DPC database. Time-to- major ICH bleeding will be defined as the number of days from the index date to the occurrence of the first major ICH bleeding event.		
Major GI bleeding event after index date	Outcome (secondary endpoint)	Any GI bleeding after index date will be identified using hospital claims which had a GI bleeding diagnosis code as the first listed ICD-10 or disease code (Appendix, 10.3.4). Time-to-any GI bleeding will be defined as the number of days from the index date to the occurrence of the first any GI bleeding event.		

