2.1. STUDY DESIGN

This is a retrospective observational study using data from Medical Data Vision Co. Ltd. (MDV Co. Ltd.) database (data set from 1 March, 2011 to 31 Jun, 2021). Among patients registered in the database, patients are selected based on the inclusion and exclusion criteria (see below).

Study measures include: (1) for safety evaluation: major bleeding (primary safety endpoint, defined as any bleeding requiring hospitalization for treatment); (2) for effectiveness evaluation: a composite of ischemic stroke, hemorrhagic stroke or SE (primary effectiveness endpoint).

The primary purpose of this study is to investigate the safety and effectiveness of apixaban compared to warfarin in patients who are prone to bleeding, with at least one known risk factor for bleeding. The analyses will be conducted using the 3-step procedure shown below,

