4.1.3. Definitions

4.1.3.1. Follow-up period

Follow-up time period starts from the next day of the index date, and ends depending on following outcomes which observed first.

- 1. Major bleeding when the target outcome for the analysis is major bleeding.
- 2. Composite of (ischemic or hemorrhagic) stroke and SE when the target outcome for the analysis is the composite endpoint.
- 3. Discontinuation of apixaban or warfarin: The index treatment will be considered to be "discontinued" if apixaban or warfarin is not prescribed within 45 days after prescription refill date (calculated from the last refill date plus days of supply) of apixaban or warfarin, even though the patient has >1 medical encounter records after more than 45 days following the prescription refill date. The supposed prescription refill date is regarded as the last day of the follow-up for discontinued patients.
- 4. Switching from apixaban or warfarin: The index treatment is regarded as "switched" if the OAC is prescribed within 45 days after prescription refill date of apixaban or warfarin when the patient has 1> medical encounter records after more than 45 days following the prescription refill date. The switched day is regarded as the last day of the follow-up for the switched patients.
- 5. Withdrawal from the database: The patients are regarded as "withdrawal" from the database if apixaban or warfarin is not prescribed within 45 days after prescription refill date of the apixaban or warfarin and there is no data of the patient on the database after prescription refill date. The last medical encounter is regard as the last day of the follow-up for patients withdrawn from the database.
- 6. An elapse of 2 years from the index date without any of the event above.

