5. ENDPOINTS AND COVARIATES

5.1. EFFICACY/EFFECTIVENESS ENDPOINT(S)

Variable	Role	Operational definition		
Stroke/SE (composite) event after index date	Outcome (primary endpoint)	Operational definition of Stroke and SE will follow the operational definition of Stroke event after index date and SE event after index date. Time to events will be defined as the number of days from the index date to the occurrence of the first stroke or SE.		
Ischemic stroke event after index date	Outcome (secondary endpoint)	Ischemic stroke after index date not including the index date will be identified using hospital claims which had an ischemic stroke diagnosis code as the first listed ICD-10 diagnosis code (Appendix, 10.3.3). An event occurrence of ischemic stroke is defined as a case that "01: Disease name which input the most medical resources", "02:Sub-disease name", "11: Main disease name", "21: Disease name behind hospitalization", or "31: Disease name which input the second most medical resources" in DPC database. Time to ischemic		

Variable	Role	Operational definition	
		stroke will be defined as the number of days from the index date to the occurrence of the first ischemic stroke.	
Hemorrhagic stroke event after index date	Outcome (secondary endpoint)	Hemorrhagic stroke after index date not including the index date will be identified using hospital claims which had a hemorrhagic stroke diagnosis code as the first listed ICD-10 diagnosis code (Appendix, 10.3.3). An event occurrence of hemorrhagic stroke i defined as a case that "01: Disease name which input the most medical resources", "02:Sub-disease name", "11: Main disease	
SE event after index date Outcome (secondary endpoint)		SE after index date not including the index date will be identified using hospital claims which had a SE diagnosis code as the first listed ICD-10 diagnosis code (Appendix, 10.3.3). An event occurrence of SE is defined as a case that "01: Disease name which input the most medical resources", "02:Sub-disease name", "11: Main disease name", "21: Disease name behind hospitalization", or "31: Disease name which input the second most medical resources" in DPC database. Time to SE will be defined as the number of days from the index date to the occurrence of the first SE event.	

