Alcohol abuse	Sub-group identifier	Baseline period	Dichotomous variable equals 1 if there are ≥1 diagnoses for Alcohol abuse ICD-10 or disease codes during the baseline period.
Bleeding diagnosis	Sub-group identifier	Baseline period	Dichotomous variable equals 1 if there are ≥1 diagnoses for major or any bleeding ICD-10 or disease codes during the baseline period

Variable	Role	Data source(s)	Operational definition	
Peptic ulcer diagnosis	Sub-group identifier	Baseline period	Dichotomous variable equals 1 if there are ≥1 diagnoses for peptic ulcer ICD-10 or disease codes during the baseline period	
Hemorrhagic stroke diagnosis	Sub-group identifier	Baseline period	Dichotomous variable equals 1 if there are ≥1 diagnoses for hemorrhagic stroke ICD-10 or disease codes during the baseline period	
Low body weight (<40 kg)	Sub-group identifier	Baseline period	Body weight during baseline period	
Polypharmacy	Sub-group identifier	Baseline period	Dichotomous variable equals 1 if there are ≥ 6 prescriptions of oral drug ATC or receipt codes during the baseline period.	
PT-INR (Prothrombin time- international normalized ratio)	potential confounder	Baseline period	Continuous variable. * Only available for patients treated with warfarin	
Physician specialty	potential confounder	Index date	Dichotomous variable equals 1 if a physician specialty on the index date is categorized into a cardiac specialty and 0 if others. Following specialties will be categorized as the cardiac specialty: cardiology stroke, cardiovascular surgery, pediatric cardiology, neurosurgery, cardiovascular medicine, and neurology. If there are ≥ 1 specialties but including the cardiac specialty, the physician specialty will be regarded as the cardiac specialty.	
Hospital size (<500 beds or not)	potential confounder	Index date	Dichotomous variable equals 1 if hospital size on the index date is <500 beds and 0 if ≥500 beds.	
Hospitalization status on index date	potential confounder	Index date	Dichotomous variable equals 1 if hospitalization status is inpatient and 0 if outpatient.	
INR (warfarin cohort)	Baseline characteristic	Baseline period	Continuous variable. * Only available for patients treated with warfarin	
Apixaban dose (2.5 g BID)	Baseline characteristic	Baseline period	2.5 mg BID or 5mg BID * Only available for patients treated with apixaban	

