10.3.3. Effectiveness endpoints

Disease	ICD10 code	Standard disease code	Note
	I60		
Hemorrhage	I61		
stroke	I62		Exclude non-traumatic extradural haemorrhage
	I63		
		3489032	
		4371003	
		4379014	
Ischemic stroke		3448002	
		3448028	
		3489029	
		3489035	
		4379006	
	H340		
	G450		
TIA	G451		
	G458		
	G459		
	I740		Include only abdominal aortic embolism
	I741		Include only aortic embolism
	I742		Include only acute arterial occlusive disease of arteries of
			upper extremities
Systemic embolism	I743		Include only femoral arterial occlusion and acute arteria
			occlusive disease of arteries of lower extremities
	I744		
	I745		Include only iliac artery embolism
	I748		Include only hepatic artery embolism
	I749		Include only thromboembolism, embolic infarction, aorti
			embolism

Page 43 of 56

Disease	ICD10 code	Standard disease code	Note	
	I748		Include only subclavian artery stenosis	

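### Major bleeding counts only as the reason for an admission, so a bleed arising during an inpatient initiation stay is never counted, although the stay is time at risk; the same intracranial hemorrhage can count as a stroke.

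*SAP*

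**What the plan says.** SAP 2.1 gives the concept of major bleeding: "primary safety endpoint, defined as any bleeding requiring hospitalization for treatment". SAP 5.2 puts it into operation through one DPC field: "An event occurrence of major bleeding is defined as a case that '21: Disease name behind hospitalization' in DPC database". The major ICH row ("Major ICH bleeding after index date will be identified using hospital claims which had an ICH bleeding diagnosis code") carries the same field-21 condition.

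The index date (SAP 4.1.3.2) is the day the drug is initiated, and "Follow-up time period starts from the next day of the index date" (SAP 4.1.3.1). No rule delays risk time to discharge or leaves out inpatient starters. They are expected in the cohort, because SAP 5.4 defines a variable for the index date: "Dichotomous variable equals 1 if hospitalization status is inpatient and 0 if outpatient". Its role there is potential confounder, but it is absent from the propensity list in SAP 7.1.1.

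Hemorrhagic stroke, part of the primary effectiveness composite, is found differently. SAP 5.1 says "Hemorrhagic stroke after index date not including the index date will be identified using hospital claims", and then "An event occurrence of hemorrhagic stroke i defined as a case that '01: Disease name which input the most medical resources', '02:Sub-disease name". Field 11 is also legible before the row breaks off in the text available to me. The ischemic stroke and SE rows list fields 01, 02, 11, 21 and 31.

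**The concern.** Take a patient admitted for heart failure who starts warfarin or apixaban on the ward and bleeds on day 5. Field 21 of that stay is heart failure, so the bleed is not a major bleed. The patient's days on the ward still enter the person-time, the Cox risk sets and the Kaplan-Meier curve. Only a later admission for bleeding can give this patient the primary safety event.

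Two things are at stake. The first days of treatment are thinned out of the safety numerator but kept in the denominator, which affects the rates and possibly the hazard ratio. And if the day-5 bleed is intracranial, it can be a stroke/SE event while it is neither a major bleed nor a major ICH. The two primary endpoints would then treat one hemorrhage in different ways, and the report could show more hemorrhagic strokes than major ICHs.

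**Working it through.** **The plan's own figures.** With HR 0.7, two-sided 0.05, power 0.80 and 1:1 allocation, events = 4 × (1.960 + 0.842)² / (ln 0.7)² = 246.8 (SAP 7.1.9: 246). Patients = 246 / ((3.77% + 2.50%)/2) = 7,847 (SAP: 7,846). These figures reproduce.

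**Inputs the documents do not give.** The share of inpatient starters, the remaining stay, the mean follow-up and the early hazard are all missing. SAP 2.1.2 gives about 20% inpatients, but for the whole database. Assumed ranges: inpatient share s = 20% to 50%; remaining stay L = 7 to 30 days; mean follow-up T = 0.5 to 2 years; hazard during the first L days k = 1 to 3 times the later hazard.

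**Formulas.** Share of bleeds that cannot be counted: f = s·k·L / (k·L + T − L). Because follow-up time is unchanged, observed HR ≈ true HR × (1 − f_apixaban) / (1 − f_warfarin). The true HR is taken as 0.70.

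**Equal stays, shares of 20% and 50%.** The last two columns put the 50% share first on warfarin, then on apixaban.

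| T, L, k | f at 20% | f at 50% | HR, more inpatients on warfarin | HR, more inpatients on apixaban |
|---|---|---|---|---|
| 2 y, 7 d, 1 | 1.4/730.5 = 0.2% | 3.5/730.5 = 0.5% | 0.70 × 1.003 = 0.702 | 0.70 × 0.997 = 0.698 |
| 1 y, 14 d, 1 | 2.8/365.25 = 0.8% | 7/365.25 = 1.9% | 0.70 × 1.012 = 0.708 | 0.70 × 0.988 = 0.692 |
| 1 y, 14 d, 3 | 8.4/393.25 = 2.1% | 21/393.25 = 5.3% | 0.70 × 1.034 = 0.724 | 0.70 × 0.967 = 0.677 |
| 0.5 y, 30 d, 3 | 18/242.6 = 7.4% | 45/242.6 = 18.5% | 0.70 × 1.137 = 0.796 | 0.70 × 0.880 = 0.616 |

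**Unequal stays as well.** Here mean follow-up is 274 days and the raised hazard covers the first 30 days. The denominator is 274 for k = 1 and 30 × 3 + 244 = 334 for k = 3.

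- 50% for 14 days against 30% for 7 days, k = 1: 7/274 = 2.6% and 2.1/274 = 0.8% missed. HR is 0.71 if warfarin has the longer stays and 0.69 if apixaban does.
- The same with k = 3: 21/334 = 6.3% and 6.3/334 = 1.9%. HR 0.73 or 0.67.
- 60% for 21 days against 30% for 10 days, k = 3: 37.8/334 = 11.3% and 9/334 = 2.7%. HR 0.77 or 0.64.

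**Equal shares and stays.** The HR is unchanged but the rates fall. With 50% inpatient starters, 14 days and 1 year, 3.77 and 2.50 %/year become 3.70 and 2.45 (k = 1) or 3.57 and 2.37 (k = 3).

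**Power.** With 50% inpatient starters, 14 days and 1 year, the 246 events become 241 (k = 1) or 233 (k = 3), and power is 0.79 or 0.78. The feasibility check found more than 10,000 patients per arm against 7,846 needed in total, so power is not the issue.

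**Stroke against ICH.** The SAP 10.3.3 stroke codes are I60, I61 and I62, with the note "Exclude non-traumatic extradural haemorrhage". The SAP 10.3.4 intracranial list covers largely the same codes but goes from I611 to I613. A hemorrhage coded I612 falls under I61 for stroke and is missing from the ICH list. Two separate mismatches follow, one of fields and one of codes.

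**The case against.** **The definition is deliberate.** Field 21 implements the concept in SAP 2.1, bleeding that requires admission. This stands: leaving out in-hospital bleeds is a design choice, not an error. What remains is that days already spent in hospital are counted as time at risk for an event that a bleed arising on those days cannot become.

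**Adjustment may reach it.** A reader might infer that, because inpatient status is outside the propensity list, nothing in the analysis deals with it. The documents do not support that. SAP 7.1.6 adds unbalanced variables to the Cox model, and the summary table in 7.2.3 points to section 5.4 for covariates. Whether this variable is checked is unclear: 7.1.2 and 7.1.3 speak of baseline covariates and characteristics, and 5.4 gives it another role. Adjustment could reduce bias from unequal inpatient shares. It cannot recover uncounted bleeds or correct for unequal stays.

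**The stay is not strictly event-free.** A reader might infer that no inpatient starter can have an event before discharge. The SAP has no rule for dating an event to admission, diagnosis or claim. A patient admitted for a bleed who starts the drug in that stay has the bleed in field 21 and could be counted, depending on dating. The supported statement concerns bleeds that arise during the stay.

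**The direction is open.** It is tempting to assume longer stays on warfarin and so a bias toward the null. The documents say nothing on stay by drug, and the mirrored cases are equally possible. Heparin use, heart failure, prior stroke or SE and cardioversion are in the propensity list and may act as partial proxies.

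**The shift is mostly small.** At 246 events a 95% interval around 0.70 is exp(ln 0.70 ± 1.96 × 2/√246), or 0.55 to 0.90. A shift of 0.01 is minor beside that. This stands for the moderate cases.

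**Conclusion.** The mismatch follows from the text. A bleed arising during an inpatient initiation stay cannot be a major bleed or major ICH, while the stay is counted as time at risk. Rates are understated whenever there are inpatient starters who bleed in hospital. The hazard ratio is biased only if inpatient share, remaining stay or in-hospital bleeding differs between arms, and then in either direction.

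The documents cannot fix the size. Across the assumed ranges with equal stays, 0.2% to 18.5% of bleeds are lost. The HR factor is 0.988 to 1.012 in the moderate case (20% against 50%, 14 days, 1 year, constant hazard). It reaches 0.88 to 1.14 only with 30-day stays, half a year of follow-up and a threefold early hazard. This is worth correcting in the SAP but is not a demonstrated distortion of the primary result. The different handling of one intracranial hemorrhage by the two primary endpoints needs no assumption; it follows from the fields as written.

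**What to change.** Keep the primary time zero and the field-21 definition. Moving the primary start to discharge would select on survival and persistence after treatment began, and weights estimated at the index date need not balance those who remain.

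1. Add inpatient status on the index date to the propensity score in SAP 7.1.1. This balances the share of inpatient starters, not the length of their stay.
2. Add a sensitivity analysis of major bleeding restricted to outpatient starters. It shows directly whether the issue matters.
3. If discharge dates are available (the documents do not say), add an analysis that starts risk time the day after discharge for inpatient starters and counts only later admissions. State that it selects on survival and persistence to discharge.
4. Add a sensitivity analysis that counts ICH from the same DPC fields as hemorrhagic stroke, with the code lists in 10.3.3 and 10.3.4 aligned, including I612. Matching the fields alone would not make every hemorrhagic stroke an ICH.

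The cost is SAP wording and a little extra analysis. Items 1, 2 and 4 use variables and diagnosis fields that the SAP already defines. The restricted analyses are less precise.

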8. RESEARCH QUESTION AND OBJECTIVES

The research questions are:

- 1. Are there any differences in the risk of major bleeding between apixaban and warfarin for patients with higher bleeding risk(s) in the general practice settings in Japan?
- 2. Are there any differences in the risk of stroke/systemic embolism between apixaban and warfarin for patients with higher bleeding risk(s) in the general practice settings in Japan?

The primary objective of the study is to compare effectiveness (a composit risk of stroke/SE) and safety (major bleeding events) of warfarin and apixaban among NVAF patients with at least one bleeding risk (that is, patients at higher risk of bleeding)

The secondary objectives are:

- 1. to compare the risk of major gastrointestinal or intracranial bleeding between warfarininitiators and apixaban-initiators in patients with at least one bleeding risk.
- 2. to compare the risk of ischemic stroke, hemorrhagic stroke or SE between warfarininitiators and apixaban-initiators in patients with at least one bleeding risk.

Objectives of other exploratory analysis are to explore the risk of major bleeding and stroke/SE in the specific populations at higher bleeding risk(s).

In this study, predetermined high bleeding risk subgroups are 1) patients with hypertension diagnosis, 2) patients with liver dysfunction, 3) patients with renal dysfunction diagnosis, 4) patients with a history of beleeding, 5) patiens with hemorrphagic stroke, 6) patients with alcohol abuse, 7) patients with concomitamt used of antiplatelet drugs, 8) patients with chronic (continuously for longer than 90 days) comcomitant use of NSAID, 9) highly elderly (> 80 years old), 10) patients with refractory hypertension, 11) patients with a history of peptic ulcer diagnosis, 12) patients with active cancer, 13) patients with diabetes mellitus, 14) patients whose body weight is <40kg, 15) patients with polypharmacy.

In the previous feasibility analysis, we found that the numbers of patients with hemorrhagic stroke, alcohol abuse, chronic concomitant used of NSAIDs (for continuously > 90 days), and refractory hypertension were less than 2,000. Due to the insufficient statistical power, we will not include these subgroups for the future analysis.

Subgroups to be analyzed for exploratory analysis will be described in a SAP.

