2.1.2. Data source

The analysis will be based on administrative data from MDV Co. Ltd., a longitudinal database based on health insurance claims and medical records obtained from the hospitals in which the DPC payment system for utilization of both inpatient and outpatient hospital claims (percentage of inpatients is about 20%). The database provides claims data from 449 hospitals (as of Aug 2021) using the DPC system for medical service claims (26% of general hospitals in Japan is under the DPC system) including approximately 36.7 million patient data.

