2.2.3. The secondary objectives are

- 1. To compare the risk of major gastrointestinal or intracranial bleeding between warfarininitiators and apixaban-initiators in patients with at least one bleeding risk.
- 2. To compare the risk of ischemic stroke, hemorrhagic stroke or SE between warfarin-initiators and apixaban-initiators in patients with at least one bleeding risk.

F

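### SAP 5.2 labels a secondary endpoint Major GI bleeding but defines it as any GI bleeding, without the hospitalization condition in the major bleeding and major ICH rows

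*SAP*

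**What the plan says.** SAP 5.2 has three safety rows.

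- **Major bleeding (primary)** and **Major ICH bleeding (secondary)**: each starts from a first-listed code on hospital claims. Each then adds that an event is a case in DPC field 21, "Disease name behind hospitalization".
- **Major GI bleeding (secondary)**: "Any GI bleeding after index date will be identified using hospital claims which had a GI bleeding diagnosis code", again as a first-listed code from Appendix 10.3.4. The time variable runs to the "occurrence of the first any GI bleeding event". The row then ends. It has no field-21 sentence.

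Elsewhere the endpoint is major GI bleeding throughout. Protocol 8 sets the secondary objective "to compare the risk of major gastrointestinal or intracranial bleeding" between the two initiator groups. SAP 2.2.3 repeats it: "To compare the risk of major gastrointestinal or intracranial bleeding". The summary table in SAP 7.2.3 plans a Cox model, a Kaplan-Meier plot and an incidence rate under the label Major GI bleeding. SAP 2.1 explains what major means for the primary safety endpoint: "defined as any bleeding requiring hospitalization for treatment".

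**The concern.** Section 5.2 is the operational definition from which the endpoint will be programmed. As written, it gives a different event from the one its label and the objective name. A programmer who follows it produces any GI bleeding under the heading Major GI bleeding. A programmer who corrects it silently departs from the written SAP.

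Three things are at stake for this endpoint. Secondary objective 1 would not be answered for its GI part. GI and intracranial bleeding would both be reported as major, but on different definitions. And a GI event could count as major without being an event in the primary major bleeding endpoint.

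**Working it through.** The plan gives no sample size, power or event figure for GI bleeding, so there is no figure to reproduce. The check is a comparison of text, plus a count of codes.

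**Step 1: which DPC fields does each endpoint row name?** The composite stroke/SE row refers to its components and is not counted. Six single-event rows remain.

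| Row | SAP section | DPC fields named |
|---|---|---|
| Ischemic stroke | 5.1 | 01, 02, 11, 21, 31 |
| Hemorrhagic stroke | 5.1 | 01, 02, 11 (the available text breaks off there) |
| SE | 5.1 | 01, 02, 11, 21, 31 |
| Major bleeding | 5.2 | 21 |
| Major ICH bleeding | 5.2 | 21 |
| Major GI bleeding | 5.2 | none |

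Field 31 is "Disease name which input the second most medical resources". Five of six rows name at least one field. The GI row is the only one that names none.

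**Step 2: could text have been lost from the row?** This is unlikely. The row runs from identification to time-to-event without a break. The word *any* stands in it three times: in the identification, in the name of the time variable, and in the first-event clause.

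**Step 3: does another passage supply the condition?**

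- *Hospital claims.* SAP 2.1.2 describes a database for "utilization of both inpatient and outpatient hospital claims (percentage of inpatients is about 20" per cent). Hospital claims alone therefore do not imply admission. The major bleeding and ICH rows also start from hospital claims and still add field 21.
- *Appendix 10.3.4.* It lists codes and adds no rule about admission or field.
- *The word any.* The documents do not use it as a synonym for major. Protocol 9.3 lists major bleeding and any bleeding as separate outcomes, and the bleeding subgroup identifier in SAP 5.4 names the two as alternatives.
- *A separate any-GI endpoint.* SAP 5.3 lists no other endpoints, so the wording has no other home.

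**Step 4: how do the code lists relate?** Appendix 10.3.4 has 18 GI codes and 27 ICH codes. Compared with Appendix 10.3.5, 18 of 18 and 27 of 27 are present. At code level, then, the GI and ICH lists lie inside the major bleeding list. In the GI row, however, only the code has to match. A bleed with a first-listed GI code that is not in field 21 meets the GI definition and fails the major bleeding definition.

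**The case against.** The best defence is that the intent is plain. The row's label, both statements of the objective and the analysis table all say major, and SAP 2.1 defines major bleeding by hospitalization. That definition itself contains the word any, so the word is not foreign to the authors' idea of major bleeding. One could argue that a sensible programmer would carry the condition over.

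The point about intent stands, and it is why this is best read as a drafting slip. It does not cure the row. The SAP 2.1 definition is attached to the primary safety endpoint. The ICH row, a secondary endpoint in the same position, repeats the condition and does not rely on SAP 2.1.

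It is also fair to say that no passage explains how an outpatient claim carries a first-listed code. That outpatient GI bleeds would enter is a reasonable reading of SAP 2.1.2, not something the plan states.

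Two stronger inferences are tempting and are not supported:

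- A reader might infer from the inpatient share of about 20% that most events counted here would be outpatient bleeds. That figure describes the database. The documents do not give the share of GI bleeds treated without admission.
- A reader might infer from the code counts that adding field 21 guarantees that every major GI event is also a major bleeding event. The match holds at code level only. Appendix 10.3.5 selects by disease name. Appendix 10.3.6 shows such limits for bleeding history at K228, K260 and S068, while Appendix 10.3.4 prints those codes without any limit. The same caution applies to ICH, because S068 is on the ICH list.

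**Conclusion.** The inconsistency is real and should be corrected before the endpoint is programmed. The row labelled Major GI bleeding defines any GI bleeding and lacks the field-21 condition of the other two safety rows. Nothing else in the documents supplies it.

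The scope is narrow: one secondary endpoint and its three planned outputs. The primary endpoints are defined in other rows, and SAP 7.1.9 sizes the study on those alone, so neither is affected. No shift in a hazard ratio or event count is claimed, because the documents contain nothing from which to estimate one.

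The practical consequence rests on two assumptions: that SAP 5.2 is followed literally, and that some first-listed GI codes occur outside field 21, whether on outpatient claims or in other disease-name fields.

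**What to change.** Rewrite the GI row in SAP 5.2 on the pattern of the ICH row, in three parts:

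1. Identify major GI bleeding after the index date from hospital claims with a first-listed GI code from Appendix 10.3.4.
2. Count it as a major GI bleeding event only when the diagnosis is in DPC field 21, "Disease name behind hospitalization".
3. Define the time variable as days from the index date to the first major GI bleeding event, and remove *any* from all three places.

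If any GI bleeding is also of interest, list it under its own name in SAP 5.3.

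The editing cost is one row, using wording the SAP already contains. The statistical cost is fewer GI events and a wider confidence interval for this secondary endpoint, in exchange for a result that matches its label and objective.
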